#### 3.2 The role of functional imaging

Functional imaging modalities such as breast MRI and nuclear breast imaging (NBI) require IV contrast injections and provide information on abnormal vascular architecture and increased vessel wall permeability that is common in BC [7]. Breast MRI is the most extensively researched among the functional modalities and serves as the gold standard for evaluation of new imaging modalities. MRI shows the highest sensitivity in detecting additional malignant lesions in the affected breast and the contralateral breast [2, 8-10]. MRI is also the most accurate modality for the evaluation of the index cancer size, while the conventional imaging modalities used for the first line of cancer staging- mammography and ultrasound- only modestly correlate with the tumor size on pathology [2, 11]. These attributes of MRI contribute to improved outcomes of surgical

treatment of BC, in particular, to the decreased need for re-excision for positive margins [2, 12, 13]. At the same time, MRI has a high rate of false positive results that require additional biopsies and may delay cancer treatment [14, 15].

Additional limitations of MRI include high cost, long scanning time, and limited availability of equipment. There is also a significant patient acceptance factor [16]. In one large study, only 51.6% of patients who were offered MRI at no cost agreed and successfully completed the MRI study. The main reasons for patient refusal were claustrophobia and time constraints [17].

Dedicated nuclear breast imaging (NBI) is a group of functional imaging modalities that depict the distribution of radioactive tracers injected into the patient. This group includes breast specific gamma imaging (BSGI), molecular breast imaging (MBI), and positron emission mammography (PEM) [18]. The role of NBI is evolving. The positive predictive values (PPVs) of MBI and BSGI in cancer detection are reported at 35-60% and are not affected by breast density, but are affected by lesion size, detecting 71% of lesions less than 5 mm in size, as opposed to 84-99% of larger tumors.

The disadvantages of NBI are long scanning time, relatively low resolution, whole-body radiation, and limited visualization of the prepectoral tissues. Yet NBI may be a viable diagnostic option for eligible women who cannot tolerate MRI [18].

### 3.3 Contrast Enhanced Mammography

CEM is a relatively new imaging technique that is based on mammography (MG) but utilizes intravenous contrast that adds functional information to morphologic information. Each CEM study has two components. The first component is a set of low-energy (LE) images, which are equivalent to non-contrast MG and are interpreted as FFDM, providing all the benefits of conventional mammography. A set of highenergy images are also obtained, above the k-edge of iodine (i.e. > 33 kVp). Then processing is performed to subtract the low-energy from the high-energy images and thereby create the second component, subtracted contrast images (SCI), which reflect only areas of enhancement. Enhancement shows the functional state of the tissues, i.e. tissue vascularity and blood vessel permeability that is similar to MRI.

CEM improves the diagnostic accuracy of MG alone, and even performs better than MG combined with DBT or MG with US [19-22]. CEM has been shown to be similar in sensitivity, but higher in specificity, than MRI for detection of index BC [19, 23]. It also efficiently finds multicentric and multifocal BC, as well as cancer in the contralateral breast with similar sensitivity but higher specificity than MRI [19, 24]. The higher specificity may make CEM more desirable than MRI in pre-operative cancer staging, since the high false positive rate currently limits the use of MRI [25].

CEM is also significantly faster and significantly less costly than MRI [16]. It can be easily incorporated into the workflow without any added work-up time. In addition, CEM is preferred over MRI by patients [22].

The main concerns raised about CEM are the need for intravenous iodinated contrast administration and the associated risk of contrastrelated complications, as well as increased radiation exposure. However, in a recent (2019) systematic literature review of CEM technique involving 14,012 patients, only 30 adverse reactions were reported, of which 26/30 were mild (pruritus, hives, etc, that resolved promptly without treatment); 3/30 cases were moderate (nausea, vomiting, urticaria etc, resolved after antihistamines or corticosteroids); and 1/30 cases was severe, non-fatal, requiring short-term intensive care [26].

As routinely performed, the radiation dose from CEM is approximately 2.3 mGy for a combination of 2 exposures. This is 1.5 times higher than a single exposure of FFDM, but is 25% lower than a combination mode mammography, which is the current standard of care at MDACC and consists of FFDM and DBT exposures. It is also significantly below the FDA allowed maximum glandular dose of 3 mGy per one exposure [27-29], [personal communication with GE Healthcare engineering team].

Until recently, no direct method of tissue sampling under direct CEM guidance existed, which made it impossible to biopsy CEM-only detected lesions, and often required performing breast MRI to search for a correlating lesion and for biopsy guidance [30]. This has changed with the introduction of the first commercially available CEM-guided biopsy device (GE Healthcare Pristina Serena Bright), which has obtained 510(k) clearance by the Food and Drug Administration in June 2020. This enables direct biopsy of CEM- only detected lesions without the need for MRI and MRI- guided biopsies that increase cost and delay patient care (Appendix A).

### 3.4 Multiparametric cohort

We are proposing to add comprehensive multiparametric data collection on the study cohort that could aid in patient stratification [ongoing MERIT study (PA17-0584)]. This would involve administering a questionnaire, collecting blood samples, and archiving raw mammographic images, for blood and imaging biomarkers discovery and validation. The analysis of the multiparametric data may provide additional predictive and prognostic information on BC patients, which could be helpful in the choice of therapy and follow-up.

### 3.5 INNOVATION

The use of CEM as a first line modality in the evaluation of breast cancers diagnosed at OSF has not been studied. Our proposed protocol may prove beneficial for improving the time and cost-efficiency of imaging work-up, as well as for the overall optimization of workflow for the benefit of the

*unique population of patients referred from OSF to MD Anderson Cancer Center.* 

# 4.0 Study Endpoints\*

4.1 Primary study endpoint:

Accuracy of CEM for incremental cancer detection in the ipsilateral and contralateral breasts. For the purpose of the study, up to 4 additional biopsy sites will be included in the analysis.

[figure not shown]
- 4.2 Secondary study endpoints:
  - Sensitivity, specificity, positive and negative predictive value of CEM, LE images, DBT, and ultrasound compared to pathology measurements as the ground truth.
  - The difference of the largest measurement of the index cancer on *LE*, *CEM*, *DBT* and *US* compared to pathology.
  - Incremental cancer detection rate provided by CEM, DBT and US.
- 4.3 Exploratory Endpoints:
  - *Rate of breast MRI utilization and the corresponding diagnosis in the study cohort.*
  - *The fraction of CEM biopsies that achieve adequate sampling of the target.*

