# 3.0 Background\*

3.1 *Current MDACC practice protocols* 

As a major tertiary cancer center, MD Anderson Cancer Center has a significant population of patients who present for staging of known breast

cancer (BC) which was already diagnosed at an outside facility (OSF), or who have OSF imaging findings that are assigned category 5 (highly suspicious with the probability of malignancy >95%) or 4C (suspicious with the probability of malignancy 50-95%) according to the American College of Radiology (ACR) Breast Imaging Reporting and Database System (BI-RADS) on OSF imaging [1]. Precise delineation of the extent of disease in the affected breast and evaluation of the contralateral breast are crucial for surgical treatment planning in BC patients [2]. Even in patients with no known BC, a second opinion at a specialized cancer center can make a significant impact on clinical management, changing the original interpretation in 36-47% of lesions [3, 4]. In patients who present with known BC at MDACC, the rate of upstaging upon second opinion interpretation and possible re-imaging is 25%, which changes surgical management in 12% of patients [5]. At the same time, the reoperation rate after breast conservation surgery in BC patients is 19% [5]. This is suboptimal and may be due to underestimation of tumor size, but this rate is lower than the national rate, which reaches 30% [2].

The current protocol for staging of OSF BC cases consists of a second read of interpretable OSF mammograms or repeating technically suboptimal mammograms, followed by ultrasound, ultrasound-guided and/or stereotactic-guided biopsies, when indicated. Some patients also require breast MRI with second look ultrasound and ultrasound- or MRIguided biopsies, which prolongs work-up and delays treatment.

At our institution, using ultrasound and MRI almost doubles the number of additional suspicious breast lesions found on mammography. 45% of these additional lesions are malignant. The sensitivities of mammography (MG), US, and MRI are 36, 71, and 85%, respectively, and their specificities are respectively 76, 68, and 39%, making MRI the most sensitive, and the MG the most specific modality. 18% of additional malignant lesions at MDA are found on MRI only [6]. Unfortunately, the need for breast MRI often delays treatment due to the limited availability of magnet time. MRI is also an expensive imaging test, further limiting access.

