### 5.6 Ground truth

Pathology results from image guided biopsies and surgical pathology results will be considered the ground truth. Breast tissue lesions will be categorized as positive if diagnosed as invasive BC or ductal carcinoma in situ (DCIS), and otherwise will be categorized as negative, including the lesions of uncertain malignant potential without subsequent surgical upgrade to invasive cancer or DCIS.

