#### Follow-up

We will follow up the study patients for at least 12 months. We will review the patients' medical records, including clinical notes, pathology, and radiology reports. This will be done to monitor for possible development of new BC or cancer recurrence. Results from biopsy and/or follow-up will serve as the ground truth and will be used to determine the true positive and true negative.

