# 12.0 Withdrawal of Subjects\*

*12.1* The patients may refuse participation at any time for any reason.

12.2 The subjects will be withdrawn from the research without their consent in the following situations:

- The patient has consented to the study but is determined to be ineligible before CEM is completed
- The patient does not complete CEM imaging
- The patient refuses a biopsy or chooses to have a biopsy at an outside *institution*
- In these cases, the patients' research files will be removed and any collected data will not be used for analysis.

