## 15.0 Data Management\* and Confidentiality

### 15.1 Statistical considerations

The primary objective of this study is to compare the accuracy of CEM and LE images (FFDM equivalent) for the detection of additional cancer sites in the affected breast and in the contralateral breast among patients with known BC diagnosed or highly suspicious at an outside facility and presenting to MD Anderson for staging imaging. The images of CEM/LE and DBT for each patient will be read/reviewed by 5 radiologists, and the majority agreement among 5 radiologists on the lexicon and BI-RADS assessment will be used for consensus. If all 5 radiologists disagree, then a consensus conference will be held. Pathology results will be considered the ground truth. Breast tissue lesions will be categorized as positive if determined as invasive cancer or DCIS, and otherwise will be categorized as negative that includes the lesions of uncertain malignant potential without subsequent surgical upgrade to invasive cancer or DCIS.

The primary outcome of this study is accuracy determined by comparing the CEM/LE results to that of the pathologic evaluations. Specifically, it is defined as the number of concordant cases between CEM/LE and pathologic evaluation divided by the total sample size. Secondary outcomes include sensitivity, specificity, negative predictive value (NPV) and positive predictive value (PPV). Sensitivity (specificity) is defined as the number of correctly diagnosed positive (negative) cases divided by the total number of confirmed positive (negative) cases, NPV is defined as the number of true negative lesions obtained from CEM/LE divided by the corresponding total predicted number of negative lesions. The PPV is similarly defined for positive breast lesions. Cancer detection rate is defined as number of invasive malignancy or DCIS divided by the total sample size.

A successful CEM guided biopsy is defined as a biopsy which successfully sampled the abnormality in question. This procedure will be considered feasible if 95% patients or more have successful CEM guided biopsy among those who will undergo this procedure, which is similar to the success rate of the prone stereotactic vacuum assisted biopsies [41].

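### No rule scores a cancer first confirmed at surgery or in follow-up at a site never biopsied, so read literally the plan overstates absolute sensitivity

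*Combined protocol and SAP*

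**What the plan says.** Four parts of the plan bear on which lesions are counted.

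- **Site selection (1.0 and 4.1).** "For the purpose of the study, up to 4 additional biopsy sites will be included in the analysis". This is the only statement of which sites enter the analysis.
- **Ground truth (5.6).** "Pathology results from image guided biopsies and surgical pathology results will be considered the ground truth". The only scoring use given for surgery is in classifying "lesions of uncertain malignant potential without subsequent surgical upgrade to invasive cancer or DCIS", that is, lesions already sampled.
- **Ground truth (Follow-up section).** "We will follow up the study patients for at least 12 months", with review of pathology and radiology reports. Then: "Results from biopsy and/or follow-up will serve as the ground truth and will be used to determine the true positive and true negative".
- **Denominators (15.1).** Sensitivity and specificity are correct calls "divided by the total number of confirmed positive (negative) cases".

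Two further items fit a biopsy-based lesion list. Section 12.2 withdraws a woman, and discards her data, where "The patient refuses a biopsy or chooses to have a biopsy at an outside" institution. The pathology items recorded under 5.7 do not include the number or location of separate foci.

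**The concern.** Take a separate invasive or DCIS focus that prompted no biopsy and first appears in the surgical specimen or during follow-up. Under 5.6 or the Follow-up section it is true disease. Under 15.1 it belongs among the confirmed positives. Under 1.0 and 4.1 it is not a biopsy site, and nothing in the plan says how it would join the lesion list.

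If the site rule is applied as written, the focus is not scored as missed by any modality, and sensitivity is measured only among cancers that some imaging test led someone to biopsy. Sensitivity is a named secondary endpoint (2.2, 4.2). It also bears on the stated goal of learning whether CEM reduces the need for MRI (2.4, 14.2), which depends on what CEM fails to show. If the choice is left open, the denominator can be settled after the results are known.

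**Working it through.** **The plan's own figure.** Section 15.2 gives 83 patients for a 12-point accuracy difference, 20% discordance, two-sided 0.05, 80% power, a mean of 1.4 lesions with variance 1, and correlations of 0.4 and 0.2.

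- Pairs: (1.960 × √0.20 + 0.842 × √(0.20 - 0.12²))² / 0.12² = 106.6.
- Design effect: 1 + ((1 + 1.4²)/1.4 - 1) × 0.08 = 1.089, taking 0.08 = 0.4 × 0.2. The formula is not printed, so multiplying the two correlations is a reading of it.
- Patients: 106.6 × 1.089 / 1.4 = 82.95, so 83.

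The figure reproduces. The point made here does not depend on it.

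**Sensitivity.** Let f be the share of all additional cancers that are confirmed only at surgery or in follow-up, at unbiopsied sites. If a modality marked none of them, true sensitivity = reported sensitivity × (1 - f). The documents do not give f; 5% and 10% are assumptions.

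- CEM, with a reported 85% assumed: 0.85 × 0.95 = 80.8%; 0.85 × 0.90 = 76.5%.
- LE, with a reported 36% (the centre's mammography figure in 3.1): 0.36 × 0.95 = 34.2%; 0.36 × 0.90 = 32.4%.

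If a modality did mark a share g of these foci, true sensitivity is reported × (1 - f) + g × f, and the overstatement is smaller.

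**NPV and accuracy.** Illustrative counts: 83 × 1.4 = 116 sites, of which 45% (3.1) are malignant, giving 52 cancers and 64 benign sites. Specificity is 76% for both modalities: the mammography figure in 3.1 for LE, assumed for CEM.

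- CEM: TP = 0.85 × 52 = 44.2, FN = 7.8, TN = 0.76 × 64 = 48.6.
- LE: TP = 0.36 × 52 = 18.7, FN = 33.3, TN = 48.6.

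Now add 5 cancers missed by both, then also unbiopsied sites that the modality correctly read as negative:

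| | Biopsied sites only | +5 missed | +5 missed, +25 true negatives | +5 missed, +50 true negatives |
|---|---|---|---|---|
| CEM NPV | 86.2% | 79.2% | 85.2% | 88.5% |
| LE NPV | 59.4% | 56.0% | 65.8% | 72.0% |
| CEM accuracy | 80.0% | 76.7% | 80.7% | 83.5% |
| LE accuracy | 58.1% | 55.7% | 63.3% | 68.6% |

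NPV and accuracy can move either way. The result depends on how many unbiopsied negatives are left out alongside the missed cancers, and the documents do not say.

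**Primary paired comparison.** A 20% discordance with a 12-point difference means 16% and 4% discordant pairs, or 18.56 and 4.64 of 116. The unclustered McNemar z is (18.56 - 4.64)/√23.2 = 2.89. Foci missed by both are concordant, so z does not change. The number added is 52 × f/(1 - f) = 2.7 at 5% and 5.8 at 10%. The difference becomes 12 × 116/118.7 = 11.7 points and 12 × 116/121.8 = 11.4 points.

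**The case against.** The best defence is that the plan excludes nothing. The sentence in 4.1 sets a cap; it does not use the word only. Section 5.6 names surgical pathology, 15.1 refers to all confirmed positives, and follow-up could hardly establish a true negative unless unbiopsied sites can count. A figure after the 4.1 sentence and the decision algorithm are not shown and may hold relevant detail. This stands as far as it goes: a reader might infer an express exclusion, and the documents do not contain one. What they lack is a rule that brings such a focus in. The follow-up sentence adds a further wording of ground truth without saying how a new site joins the lesion list.

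Misses by CEM or LE are also scored wherever another test prompted a biopsy. Section 5.3 allows for ultrasound-, stereotactic- and MRI-guided biopsy in routine care. This stands, and it makes the bias partial.

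A reader might take "18% of additional malignant lesions at MDA are found on MRI only" (section 3.1) as an estimate of f. It is not. Those cancers were detected by imaging, can be biopsied, and would then be scored as missed by CEM or LE. The figure says nothing direct about cancers that no test led anyone to sample.

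A reader might also infer that CEM is flattered relative to LE. For foci that both miss, both sensitivities scale by the same factor, so their ratio is unchanged, and the McNemar statistic does not move.

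**Conclusion.** The concern holds as an unreconciled conflict and a missing scoring rule. Sections 1.0 and 4.1, 5.6, Follow-up and 15.1 do not together say what happens to a cancer confirmed at a site never biopsied. On the literal reading, the absolute sensitivity of all four modalities is overstated by 1/(1 - f): about 4 to 8.5 points on a reported 85%, and about 2 to 4 points on a reported 36%, for f of 5% to 10%. These sizes rest on an assumed f, an assumed CEM sensitivity, and the assumption that the modality marked none of these foci.

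A reader might go further and conclude that NPV and accuracy come out too high. The documents do not support that, because unbiopsied true negatives are left out as well and the net direction is open. The primary test is essentially unaffected by foci both modalities miss. The point therefore concerns the secondary sensitivity estimates and what they are taken to show about replacing MRI.

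**What to change.** - **1.0 and 4.1:** replace *additional biopsy sites* with *additional sites with biopsy, surgical or follow-up confirmation*.
- **15.1, positives:** state that a separate invasive or DCIS focus at an unbiopsied site is a confirmed positive. Score it positive for a modality only if that modality's reading marked the location, and otherwise as a false negative. The reading is the reader consensus for LE, DBT and CEM, and the clinical report for ultrasound.
- **15.1, negatives:** state that marked but unbiopsied sites shown negative by surgery or follow-up are confirmed negatives on the same basis, so that the rule is symmetric.
- **5.6 and Follow-up:** align the two definitions of ground truth with each other and with 4.1. Follow-up also looks for new cancers and recurrences, so say which follow-up cancers count as present at staging.
- **Reporting:** give the biopsied-sites-only results as a secondary display, and state how many women had surgery.

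The cost is small. Readers already record the number, laterality and clock position of additional lesions (5.9), and pathology reports are already reviewed in follow-up. What is added is abstraction of separate foci from those reports and some location matching. Completeness will depend on the extent of surgery, and the sensitivities will look slightly less favourable. The rule should be fixed before readings are compared with pathology.

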# 5.0 Procedures Involved\*

## 5.1 PROCEDURE TO OBTAIN CONSENT

Eligible and interested subjects will be consented for study participation. A research staff member who is trained in the informed consent process will explain the study, invite the patients to enroll, and obtain the informed consent of women who wish to participate. Subjects may be enrolled using the approved MD Anderson procedures for remote consenting.

5.2 PATIENT WORKFLOW (Fig. 1)

*Fig. 1. Patient workflow. Research components are represented in blue, and standard of care components in black.* 

## 5.3 IMAGING WITH CEM

Safety checklist and IV injection:

The imaging technologist, the study personnel, and the radiologist will be responsible for ensuring the safe administration of IV contrast. IV contrast injections and eligibility screening will be performed in accordance with MDACC institutional policies. Contrast safety will be ensured by following the current UTMDACC DIVISION OF DIAGNOSTIC IMAGING POLICY # 3.30, amendment for CEM (Appendix B).

The imaging technologist and the study nurse or research coordinator will use a patient safety checklist for verifying that the patient has no contraindications for the study.

[figure not shown]
If a patient passes the safety checklist, an IV catheter will be placed in the patient's forearm or antecubital vein in the mammography suite

immediately before the procedure by a trained nurse, mammography technologist, or study coordinator. The patients will be sitting for the injection to minimize vaso-vagal reactions. Low-osmolality iodine-based intravenous contrast (Omnipaque 350 mg I/mL; GE Healthcare or equivalent) will be injected using a power injector, at a rate of 3 mL/s for a total dose of 1.5 mL/kg body weight, but not exceeding 150 ml, followed by a 30 mL saline flush [30-32].

Imaging technique:

CEM will be administered using FDA-approved equipment. The study will be conducted using a full-field digital mammography system capable of providing low- and high-energy exposures to the breast under the same compression, as well as producing subtracted contrast images, such as Senographe Pristina (GE Healthcare, Buc, FR) or an equivalent system.

1. The imaging will start with the affected breast 2 min after contrast injections and will consist of one high and one low energy exposure in succession. The affected breast will be imaged in craniocaudal (CC), mediolateral oblique (MLO), and lateromedial (LM) projections (Fig.1). CC and MLO images will also be obtained of the unaffected breast (Fig. 2).

